Title:

Cytopenias in Hospitalized patients of COVID-19 during first and other waves

Introduction:

COVID-19 is a global pandemic and since December 2019 we have seen different variants and different severity levels of this disease. Laboratory parameters has played quite an important role in diagnosis as well predicting the prognosis and disease course. The corona virus SARS CoV-2 which is responsible for the current global pandemic that has resulted in considerable morbidity and mortality¹.

COVID-19 is highly communicable disease and can lead to diversity of symptoms ranging from mild fever, dry cough, myalgias and headache to at times gastrointestinal symptoms including abdominal pain, diarrhea and vomiting ². Pakistan being at the adjacent border of China and Iran was at great threat of infiltration and two confirmed case of Corona virus were reported in city Karachi and Islamabad on February 26th 2020³. To date Pakistan Has faced more than three waves of COVID-19, the first wave span from late May to Mid July 2020, second wave spans from early November to mid December 2020 and third wave spans from Mid March 2021 to June 2021.

COVID-19 and its relationship with laboratory parameters have been well established by many studies. The clinicians might consider the hematological and biochemical parameters in the patients with COVID-19 in future decision-making. These indicators may sustain clinical decisions to recognize high fatality case and poor diagnosis in the initial admission phase⁴.COVID-19 is considered mainly to involve respiratory system, but multi systemic involvement is also seen in the evolving data from managing the patients of COVID-19. Hemopoietic system is one of them and blood count anomalies like neutrophilia and lymphopenia are particularly seen in COVID-19 patients and also have a prognostic significance⁵.NLR (neutrophil to lymphocyte ratio), MLR (monocyte to lymphocyte Ratio) And PLR be used as a useful predictive marker for the disease course as well as severity and outcome of COVID-19 patients. Systemic immune inflammatory index (SII) has a positive prognostic value⁶.

Objective:

It was observed that cytopenias are more prominent in patients during subsequent waves of COVID-19. The aim of this study was statistical verification of this observed phenomena.

Materials and methods:

Study design: Retrospective Cross-sectional study

Sample size: 202

Study Setting: Department of Pathology and Department of Medicine, FMH.

Eligibility criteria:

Inclusion Criteria:

- COVID-19 positive Hospitalized patients
- Both genders
- All ages

Exclusion Criteria:

- Know patients with Chronic liver disease
- Known patients with Hematological disorders

Materials and methods:

Clinical and laboratory data as well as outcome of total 202 COVID-19 PCR positive patients admitted in Fatima memorial Hospital, Lahore, Pakistan will be collected after IRB approval and informed consent from patient during first and other waves. Data of First wave is from May 2020 to July 2020, second wave from early November to Mid December 2020 and third wave from Midmarch to June 2021. Comparison of data on basis of SII as well hematological parameters of First Wave will be compared to other waves of COVID-19. CBC will be performed on Sysmex XN-10. WHO normal values will be taken as reference for CBC. Neutrophil to lymphocyte ratio (NLR) will be calculated as N/L And >3 will be considered as raised NLR. Platelet to lymphocyte Ratio (PLR) will be calculated as P/L. Raised PLR will be >149 for Males and >172 for females. Monocyte to lymphocyte ratio will be also calculated by M/L and >0.23 will be considered as raised value. Systemic immune inflammatory index is calculated by P x N/L. SII > 600 will be labelled as raised and bad prognostic tool.

Statistical analysis:

Continuous variables will be analyzed by Man-Whitney analysis and categorical variables will be analyzed by independent T test. All the data will be entered and analyzed in SPSS 25. P-value equal to or less than 0.05 will be considered significant.

References:

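### The aim is to verify that cytopenias are more prominent in later waves, but no cytopenia endpoint or deciding comparison is fixed, so a 5% threshold on every test does not give a 5% error rate for that claim

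*Protocol*

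**What the plan says.** The Objective (Protocol) starts from an observation with a direction: "It was observed that cytopenias are more prominent in patients during subsequent waves of COVID-19". It then sets the purpose: "The aim of this study was statistical verification of this observed phenomena". No source is given for the observation.

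Under Materials and methods, the planned comparison is broad: "Comparison of data on basis of SII as well hematological parameters of First Wave will be compared to other waves of COVID-19". The haematological parameters are not listed. Four derived indices are defined, each with a cut-off for a raised value. For the first, the rule reads ">3 will be considered as raised NLR"; the others are a PLR over 149 in men or 172 in women, an MLR over 0.23, and an SII above 600. WHO normal values are to serve as the CBC reference, but no count or lower limit is named as a cytopenia.

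The Statistical analysis section gives one test for continuous variables, another for categorical variables, and a single decision rule: "P-value equal to or less than 0.05 will be considered significant". The design is retrospective, with 202 patients from the first, second and third waves.

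**The concern.** A verification aim needs a result that, stated in advance, would confirm or fail to confirm the claim. Here a reader cannot tell which result that is. The claim concerns low counts, yet the only numerical cut-offs in the protocol mark raised ratios and a raised index. One threshold applies to every variable, with none ranked above another.

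The 0.05 threshold is therefore the error rate of each test, not of the claim. Several correlated tests bear on the claim more or less directly, and any favourable one could be presented as support. At stake is whether a report that the observation was verified would mean what a 5% threshold suggests.

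A second issue is where the observation came from. The waves compared are the same three that the Introduction describes, and nothing keeps the patients who prompted the observation out of the analysis.

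**Working it through.** **Inputs from the protocol.** Per-test threshold 0.05 (two-sided assumed; sidedness is not stated). Total sample 202. Mann-Whitney for continuous variables and a t test for categorical ones, both applied as planned.

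**Counting the tests.** The index formulas use four counts: neutrophils (N), lymphocytes (L), monocytes (M) and platelets (P). With NLR, PLR, MLR and SII, and the raised/not-raised version of each, this gives 4 + 4 + 4 = 12 tests on one contrast (first wave against later waves pooled). Haemoglobin, white cell count, low-count categories or separate second- and third-wave contrasts would add more.

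**The plan's own figure.** For one test, 1 − (1 − 0.05)^1 = 0.05. The threshold equals the error rate of the claim only when one test decides it. In one named direction it is 0.05 / 2 = 0.025.

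**If tests were independent.**
- 12 tests, either direction: 1 − 0.95^12 = 46.0%
- 12 tests, claimed direction only: 1 − 0.975^12 = 26.2%
- 4 counts, claimed direction only: 1 − 0.975^4 = 9.6%
- 7 counts, claimed direction only: 1 − 0.975^7 = 16.2%

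The tests are not independent, because the indices are built from the counts. Simulation is therefore needed.

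**Simulation with no wave difference.** Assumptions, none of them in the protocol: log-normal N, L, M and P with log-scale SDs of 0.4 to 0.5, pairwise correlation from 0 to 0.5, 55% male, and wave splits of 101/101 or 67/135. There were 2,500 simulated studies per setting. The claimed direction means lower counts, or higher indices and more raised flags, in later waves.

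| Split, correlation | 12 tests, either direction | 12 tests, claimed direction |
|---|---|---|
| 101/101, 0 | 31.3% | 18.0% |
| 101/101, 0.3 | 33.1% | 19.4% |
| 101/101, 0.5 | 34.0% | 19.0% |
| 67/135, 0.3 | 33.3% | 17.8% |

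Across runs, the either-direction figure is 31–35%. For the four counts alone, a significantly lower value in later waves on at least one of them occurred in about 8–11% of studies. A repeat with 4,000 studies per setting gave 7.9% to 9.4%, in line with the 9.6% above.

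**Relative to nominal.** Either direction: 31/5 = 6.2 to 35/5 = 7 times. Claimed direction, four counts: 8/2.5 = 3.2 to 11/2.5 = 4.4 times. Claimed direction, all 12: 18/2.5 = 7.2 to 19/2.5 = 7.6 times.

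**Sensitivity.** The protocol does not say whether the later waves are pooled. Testing wave one against two and one against three separately (67/67/68, correlation 0.3) gives 51.8% in either direction and 31.7% in the claimed direction for the 12 tests.

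**The case against.** The strongest reply has four parts.

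First, the claim is directional and about low counts. A raised SII is not a cytopenia, and a higher count in later waves would contradict the claim. A reader might infer that the chance of falsely verifying the observation is about one in three; the documents do not support that. The 31–35% is the chance of any nominally significant result. The figure closest to the claim is about 8–11%, and 18–19% applies only if raised indices are also accepted as support. This part stands and sets the size of the point.

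Second, the protocol does not say that a single p ≤ 0.05 verifies the observation. It calls such a result significant and stops there. That is correct: the weakness is that no rule is fixed, not that a bad one is stated.

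Third, the test list is partly assumed. CBC parameters are not enumerated, and the protocol does not state outright that each index will be tested both as a measurement and as a raised/not-raised variable. A multiplicity adjustment could also sit in a statistical analysis plan that is not shown, so its absence is not the point here. What remains is a mismatch within the protocol, which fixes both the verification aim and the significance rule without saying what connects them.

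Fourth, a reader might infer that the observation came from the very patients to be analysed. The protocol says only that it was observed, not where or in whom. The retrospective design and the wave dates make overlap plausible, but it is not established.

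**Conclusion.** The point holds in a limited form. As written, the protocol does not hold a 5% error rate (2.5% in the claimed direction) for the claim it sets out to verify, because no cytopenia endpoint and no deciding comparison are fixed. On one pooled contrast, the chance of a spurious result in the claimed direction is about 8–11% on the four counts and about 18–19% on all 12 tests. The chance of any p ≤ 0.05 in either direction is about 31–35%. All of these rest on the assumed test list, distributions, correlations and wave split; longer lists or separate wave contrasts raise them.

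If the patients who prompted the observation are among the 202, even one pre-named test would not hold its nominal rate. That bias is separate from the figures above and cannot be quantified from the document.

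The study remains usable. The threshold simply does not support the word verification, and this should be corrected.

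**What to change.** 1. **Statistical analysis.** Name one cytopenia comparison, first wave against later waves pooled, as the only test of the claim at two-sided 0.05. One candidate is the share of patients with at least one count below its lower reference limit, with the counts and limits written out.
2. **Statistical analysis.** Label all other parameters, indices and cut-offs as secondary. Report them as differences with 95% confidence intervals, and either adjust them by Holm's method or describe them as exploratory.
3. **Objective.** Replace the verification wording with estimating and testing the between-wave difference in the named endpoint. Add that the observation may have arisen from the same waves, since naming one test does not remove that bias.

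The cost is wording in two sections and, if chosen, one adjustment step. The claim becomes more modest and fewer secondary results will be nominally significant. No new data are needed.

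### Does the mismatch between the Introduction's and the Methods' dates for the first wave make the reference group unreliable?

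*Protocol*

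**What the plan says.** The Introduction of the protocol, describing the epidemic in Pakistan, gives three periods. The one for the reference group reads "the first wave span from late May to Mid July 2020". For the next group the wording is "second wave spans from early November to mid December 2020". The last period is described by the phrase "third wave spans from Mid March 2021 to June 2021".

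The Materials and methods text after the eligibility criteria, describing the records to be taken from one Lahore hospital, gives the periods again. The reference group now has "Data of First wave is from May 2020 to July 2020". The next group is given as "second wave from early November to Mid December 2020". The last group is put as "third wave from Midmarch to June 2021". The second and third periods repeat the Introduction. The first has lost its qualifiers for the part of the month.

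The first wave is the reference group: "hematological parameters of First Wave will be compared to other waves of COVID-19". The total is stated as "Sample size: 202", with no split by wave. No passage gives exact calendar days for any wave, and none comments on the difference.

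**The concern.** Wave of admission is the only grouping variable in this study, and the first wave enters every contrast. If its limits are unclear, so is its membership. Read literally, the Methods admit patients from early and mid May and from late July 2020, whom the Introduction would place outside the wave, while the two later groups keep to the periods given in the Introduction.

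Three things could be at stake. The reference group might mix patients from the wave with patients from its margins. The sizes of the groups within the 202 might depend on which dates are used. And because the study is retrospective and sets out to verify something already observed, two available windows might leave room to choose between them once the data are known.

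**Working it through.** The protocol states no figure for the overlap, so there is nothing of its own to reproduce. The check is a count of days, followed by the question of what the count means for the comparison.

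**Inputs**
- Methods window (Materials and methods): May to July 2020. Assumption: whole months, 1 May to 31 July.
- Introduction window: late May to mid July 2020. Assumption: start between 21 and 31 May, end between 10 and 20 July.
- Start of the next group (both sections): early November 2020, so 1 November at the earliest.

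**Step 1: length of the Methods window.** 31 + 30 + 31 = 92 days.

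**Step 2: length of the Introduction window and the part of the Methods window outside it.** Share outside = (92 − Introduction days) / 92, counting both end days.

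| Reading of the Introduction | Days | Outside | Share of days |
|---|---|---|---|
| 21 May to 20 July | 11 + 30 + 20 = 61 | 31 | 31/92 = 34% |
| 25 May to 15 July | 7 + 30 + 15 = 52 | 40 | 40/92 = 43% |
| 31 May to 10 July | 1 + 30 + 10 = 41 | 51 | 51/92 = 55% |

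**Step 3: dependence on the whole-month assumption.** Suppose the Methods wording is shorthand. Take the Introduction as 21 May to 15 July (11 + 30 + 15 = 56 days). A Methods window of 15 May to 15 July has 17 + 30 + 15 = 62 days, of which 62 − 56 = 6 (10%) lie outside. A Methods window of 31 May to 1 July has 1 + 30 + 1 = 32 days, none of them outside. The text does not say which reading was meant.

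**Step 4: from days to patients.** Let r be the daily admission rate at the margins divided by the rate inside the Introduction's span. The share of first-wave patients from the margins is r × (days outside) / [r × (days outside) + (days inside)]. With 40 days outside and 52 inside, r = 1 gives 40/92 = 43%, and the share falls towards 0 as r falls towards 0. If the Introduction places the wave correctly, r should be below 1, so 43% is an upper limit under that reading. The protocol gives nothing from which to estimate r.

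**Step 5: can anyone change group?** After 31 July come August, September and October, 31 + 30 + 31 = 92 days, before the earliest possible start of the second wave. A patient admitted at either edge of May to July 2020 is therefore either in the first-wave group or not in the study. No such patient can be counted in a later wave.

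**Step 6: what would be needed for a bias.** With p the share of marginal patients, the mean of any blood-count measure in the wide group minus its mean in the narrow group equals p × (mean at the margins − mean inside). This is zero unless marginal patients differ from the others. The protocol gives no reason to expect such a difference, and no direction for it.

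**The case for a change.** The best argument for a change is that the shorthand reading is the weaker one. The sentence that drops the qualifiers for the first wave keeps them for the second and third, which suggests that the writer used them where they were meant. A data collector working from the Methods would then take all of May and all of July. The wording also differs only for the reference group, and agreeing one pair of dates would cost a sentence and would remove any choice made after seeing the data.

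Much of this stands as a description of the text. The two statements differ, nothing reconciles them, and the literal reading of the Methods is the more natural one. But that reading also removes the ambiguity, because the Methods are then a usable rule and the Introduction's sentence is only a looser account of the national picture. A hospital may reasonably collect over a period somewhat wider than the national peak. The contrast with the later groups is also smaller than it appears: the third wave ends at month precision in both sections, and no wave has exact days.

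The argument about choosing a window afterwards has some force in a retrospective study. It requires treating a background sentence as a competing eligibility rule, however, and the protocol does not present it as one.

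**Conclusion.** The discrepancy is real but clerical, and the plan need not change. Under the whole-month reading, 34% to 55% of the calendar days in the Methods window lie outside the Introduction's span. The corresponding share of patients is unknown and would be smaller if admissions clustered in the span that the Introduction describes.

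The effect is limited to who is included at the edges of the reference group. Assignment between groups is untouched, and every patient admitted from May to July 2020 precedes the later waves, which is the ordering that the objective needs.

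The possible remedies bring no demonstrated gain. Rewording the Introduction to match the Methods would alter no result. Narrowing the Methods window could lose reference patients from a total of 202 without a shown benefit. A sensitivity analysis on the shorter span is optional.

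This conclusion assumes that the Methods dates are followed as written. It would need another look if admissions in early May or late July 2020 were known to differ materially in their blood counts from the rest of the group. The protocol contains nothing to that effect.

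### First and later waves are compared only by unadjusted two-sample tests, so a difference in cytopenias cannot be separated from a difference in age or sex mix

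*Protocol*

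**What the plan says.** The Objective starts from an impression, "It was observed that cytopenias are more prominent in patients during subsequent waves of COVID-19", and continues: "The aim of this study was statistical verification of this observed phenomena". The design is retrospective and cross-sectional, with 202 hospitalised PCR-positive patients. Materials and methods defines the waves by calendar dates and says that "hematological parameters of First Wave will be compared to other waves of COVID-19".

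The Statistical analysis section names the methods in one sentence: "Continuous variables will be analyzed by Man-Whitney analysis and categorical variables will be analyzed by independent T test". It adds the software and a significance threshold of 0.05. It mentions no covariates, stratification, matching or comparison of patient characteristics between waves.

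Three other places bear on the point:

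- Eligibility criteria admit both sexes and every age. They exclude only known chronic liver disease and known haematological disorders.
- Materials and methods gives a sex-specific cut-off for one index: "Raised PLR will be >149 for Males and >172 for females".
- The Introduction speaks of "different variants and different severity levels of this disease" over the pandemic, and calls the cell-count ratios NLR, MLR and PLR a "useful predictive marker for the disease course as well as severity and outcome of COVID-19 patients".

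**The concern.** Groups defined by calendar period are not balanced by design. With unrestricted age and sex, the patients admitted in a later wave may differ from those in the first. If age or sex is related to blood counts, such a shift can produce a difference between waves that has nothing to do with the wave.

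The protocol gives its own reason to take this seriously. It treats sex as relevant to PLR by setting different cut-offs for men and women, yet compares PLR as a continuous variable without regard to sex. The two exclusions remove other causes of cytopenia but do nothing to balance age or sex.

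What is at stake is how a significant result is read. A study that sets out to verify that cytopenias are more prominent in later waves, and then reports a crude p-value below 0.05, will readily be taken to show an effect of the wave itself.

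**Working it through.** **No figure of the plan to reproduce.** The protocol gives a total of 202 and a threshold of 0.05. It gives no split by wave, no expected rates and no age or sex distribution. Everything below except 202 and 0.05 is therefore an assumption. Tests are taken as two-sided. Two splits are used: 101/101, and 67/135 (three waves of equal size, first against the other two).

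**1. A binary cytopenia with no wave effect.** Assume lymphopenia in 50% of older and 30% of younger patients, the same in every wave. With older share *s*, the prevalence in a wave is *s* × 0.50 + (1 − *s*) × 0.30.

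- First wave, *s* = 0.30: 0.15 + 0.21 = 0.36
- Later, *s* = 0.40: 0.20 + 0.18 = 0.38
- Later, *s* = 0.50: 0.25 + 0.15 = 0.40
- Later, *s* = 0.60: 0.30 + 0.12 = 0.42

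The chance of a significant pooled two-proportion z test was found by exact enumeration of all binomial outcomes. The adjusted logistic model (wave, age group, sex; sex 50/50 with no effect) was simulated with 8,000 studies per scenario at 101/101 and 5,000 at 67/135.

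| Older share, first vs later | Crude gap | Crude test, 101/101 | Crude test, 67/135 |
|---|---|---|---|
| 30% vs 40% | 2 points | 6.0% | 5.8% |
| 30% vs 50% | 4 points | 9.1% | 8.5% |
| 30% vs 60% | 6 points | 14.4% | 13.0% |

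The adjusted model was significant in 4.5% to 5.3% of studies.

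A normal approximation confirms the last row at 101/101. The pooled standard error is √(0.39 × 0.61 × 2/101) = 0.0686, so the shift is 0.06/0.0686 = 0.87. The rejection rate is P(Z > 1.96 − 0.87) + P(Z < −1.96 − 0.87), about 0.14.

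**2. A continuous count with no wave effect.** In 2,000 simulated studies per scenario at 101/101, a two-level factor (age group or sex) shifts the count by 0.5 or 0.8 SD.

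| Factor share, first vs later | Crude Mann-Whitney, 0.5 SD | Crude Mann-Whitney, 0.8 SD |
|---|---|---|
| 50% vs 50% | 5% | 5% |
| 40% vs 60% | 11% | 18% |
| 30% vs 70% | 28% | 56% |

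Rank regression on wave and the factor stays at 4.7% to 5.8% throughout. With equal mix the crude test keeps its nominal level, so the problem is strictly conditional on imbalance.

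**3. Cost in precision.** At 101/101 the simulated standard error of the log odds ratio rises from 0.295 to 0.304 with equal age mix (0.304/0.295 = 1.03). It rises from 0.291 to 0.315 with 30% against 60% older (0.315/0.291 = 1.08). Large-sample formulae give about 2% and 7%.

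**4. Why severity is a different matter.** Assume lymphopenia in 60% of severe and 30% of non-severe cases, and a severe share of 30% against 60%. The prevalences are 0.3 × 0.6 + 0.7 × 0.3 = 0.39 and 0.6 × 0.6 + 0.4 × 0.3 = 0.48. The crude odds ratio is (0.48/0.52)/(0.39/0.61) = 1.44; adjusted for severity it is 1.00. If the later wave itself caused the greater severity, that adjustment removes a real difference.

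**The case against.** The strongest reply is that the Objective is descriptive. It asks whether cytopenias are more prominent in later-wave inpatients, and a crude test answers that. The protocol nowhere announces that a difference will be attributed to the wave independently of case mix. This stands, and is why the crude comparison should be kept. It does not remove the need to say how far the result may be interpreted.

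No imbalance is documented, and no passage links age to a blood count. That also stands. The only documentary support for sex is the PLR cut-off, which already accounts for sex when PLR is classified as raised; the gap is in continuous PLR. The concern is therefore conditional, and with a modest shift (30% to 40% older) the crude test stays near its nominal level. The adjusted model's good behaviour is also partly by construction, because it fits the same age grouping that generated the data.

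A separate analysis plan might add covariates. But the protocol does not defer its analysis: it states one, and that one is unadjusted.

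Finally, adjusting for age and sex leaves severity and admission thresholds unhandled, so it would not by itself establish a wave effect. That is true and limits what the adjusted result can claim. It does not make the crude test the better basis for attribution.

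**Conclusion.** The concern holds. The protocol fixes unadjusted two-sample tests for a non-randomised comparison of calendar periods, with age and sex unrestricted, and nothing else in it deals with patient mix. If age or sex mix differs between waves and is related to blood counts, a crude difference cannot be attributed to the wave.

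The size of the bias cannot be derived from the protocol. Under the assumed scenarios it ranges from negligible, when the mix is similar, to a false-positive rate of 14.4% for lymphopenia, or up to 56% for a continuous count under a strong imbalance (30% against 70% and an effect of 0.8 SD). The change is worth making because it is cheap, but confidence that the bias matters in these data is only moderate. The protocol's use of a t test for categorical variables is a separate matter; correcting it would not cure this one.

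**What to change.** Add a short paragraph to Statistical analysis:

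- Keep the crude comparison as the description of the observed difference, and report age and sex by wave.
- Pre-specify a regression on wave (first vs later) adjusted for age and sex: logistic for each cytopenia, linear on log-transformed counts and indices. Say in advance how age enters; a single linear term keeps the model at three terms.
- Report adjusted odds ratios or ratios of geometric means with 95% confidence intervals.
- Add admission severity only in a sensitivity model, stating that it may mediate a wave effect.
- State that a difference will not be attributed to the wave on the crude test alone.

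The cost is modest extra work in SPSS. Sex is already needed for the PLR cut-off, and age is a routine item of the hospital record. Standard errors grow by about 3% to 8% in the illustration. A rule is needed for missing severity in the sensitivity model. At the usual 10 events per term, three terms need about 30 cases (30/202 = 15%), so rarer cytopenias should be reported crude only and labelled as such.

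### The protocol assigns categorical variables to the independent t test, which compares means, and names no test of proportions; it should name chi-square or Fisher's exact test.

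*Protocol*

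**What the plan says.** The Statistical analysis section names two tests. For continuous data, "Continuous variables will be analyzed by Man-Whitney analysis"; for the rest, "categorical variables will be analyzed by independent T test". The significance rule is "P-value equal to or less than 0.05 will be considered significant", and the software is SPSS 25. Neither chi-square, Fisher's exact test nor any other test of proportions appears in the protocol.

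The second Materials and methods section compares the first wave with the other waves and sets up variables that fall under the second rule:

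- Four explicit yes/no cut-offs: NLR above 3, PLR above 149 (males) or 172 (females), MLR above 0.23, and SII, where "SII > 600 will be labelled as raised and bad prognostic tool".
- Blood counts, for which "WHO normal values will be taken as reference for CBC". The text does not say outright that counts will be dichotomised, but this is the natural basis for classing a count as a cytopenia.
- Outcome, which is collected without stated levels: "Clinical and laboratory data as well as outcome of total 202 COVID-19 PCR positive patients".

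The Objective is to verify statistically the impression that "It was observed that cytopenias are more prominent in patients during subsequent waves of COVID-19".

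**The concern.** An independent t test asks whether two means differ. A categorical variable has proportions, and it has a mean only after its categories have been given numbers. The protocol assigns the t test to all categorical variables without qualification, so any result reported as the share of patients with a raised index or a cytopenia would be tested by a method not meant for it.

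Three situations need to be kept apart:

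1. **Two levels, equal-variance t test.** The coding does not matter, and the result should lie close to chi-square.
2. **Two levels, unequal-variance t test.** SPSS prints this row beside the first. For a rare category, the smaller group will often contain no cases. Its estimated variance is then zero and the standard error is too small.
3. **Three or more unordered levels.** The p-value depends on which number is attached to which category.

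At stake are false positive findings for rare cytopenias in situation 2, and arbitrary or missed findings in situation 3. Indices and counts analysed as continuous go to Mann-Whitney, which suits them.

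**Working it through.** **Inputs.** From the protocol: N = 202, two groups (first wave against other waves), significance at p ≤ 0.05. Assumed, because not stated: two-sided tests; splits 101/101, 67/135, 50/152 and 30/172; the same true prevalence in both groups (2% to 50%). The protocol gives no figure of its own to reproduce on this point.

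**Step 1: equal-variance t test against chi-square, two levels.** With 0/1 coding the two statistics are tied by t² = (N − 2)χ² / (N − χ²). The chi-square cut-off at 0.05 is 3.841. The t cut-off with 200 degrees of freedom is 1.972, and 1.972² = 3.888, which corresponds to χ² = 202 × 3.888 / (200 + 3.888) = 3.852. The decisions differ only if χ² lies between 3.841 and 3.852. Over every possible 2×2 table:

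| Split | Tables | Different decision |
|---|---|---|
| 101/101 | 102 × 102 = 10,404 | 4 |
| 67/135 | 68 × 136 = 9,248 | 4 |
| 50/152 | 51 × 153 = 7,803 | 6 |
| 30/172 | 31 × 173 = 5,363 | 0 |
| Total | 32,818 | 14 |

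**Step 2: type I error, two levels.** Each table was weighted by its binomial probability under equal prevalence, and the weights of tables with p ≤ 0.05 were added. For the unequal-variance row:

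| Prevalence | 101/101 | 67/135 | 50/152 | 30/172 |
|---|---|---|---|---|
| 2% | 4.0% | 8.0% | 13.3% | 24.7% |
| 5% | 4.4% | 7.1% | 9.5% | 21.2% |
| 10% | 5.2% | 5.3% | 6.4% | 8.7% |
| 30% | 5.0% | 5.0% | 5.2% | 5.5% |

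The equal-variance row lies between 3.2% and 6.0% over all four splits and all prevalences from 2% to 50%. If Levene's test (p ≤ 0.05) chooses the row, the rates at 2% and 5% prevalence are 13.3% and 9.5% for 50/152, and 7.3% and 18.8% for 30/172. Chi-square, with Fisher's exact test when an expected count is below 5, stays between 0.5% and 5.7%.

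**Step 3: one table, 0/50 against 5/152.** The difference is 5/152 = 0.0329.

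- Unequal variance: the first group's variance is 0 and the second's is 0.0320. SE = √(0.0320/152) = 0.0145, t = 2.27 on 151 df, p = 0.025.
- Equal variance: pooled variance = 152 × 0.0329 × 0.9671 / 200 = 0.0242. SE = √(0.0242 × (1/50 + 1/152)) = 0.0254, t = 1.30 on 200 df, p = 0.196.
- Levene's test: p = 0.008, which directs the analyst to the unequal-variance row.
- The smallest expected count is 5 × 50/202 = 1.24, so Fisher's exact test applies: p = 0.34.

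**Step 4: a hypothetical three-level variable, 70/20/11 against 76/8/17.** Chi-square gives p = 0.036. The equal-variance t test gives:

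| Codes for the three levels | Group means | p |
|---|---|---|
| 0, 1, 2 | 42/101 and 42/101 | 1.00 |
| 0, 2, 1 | 51/101 and 33/101 | 0.080 |
| 1, 0, 2 | 92/101 and 110/101 | 0.016 |

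The other three codings are these reversed and give the same p-values.

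**The case against.** The misstatement itself is hard to dispute; the case against is that it does little harm. The comparison described in Materials and methods is of SII and haematological parameters, which can be tested as continuous by Mann-Whitney. For the dichotomies that the protocol does define, the ordinary equal-variance t test gives practically the chi-square answer. The inflation needs three conditions together: the unequal-variance row is used, the groups are clearly unequal, and the category is rare. The protocol states neither split nor prevalence, and its Introduction describes lymphopenia as particularly seen in these patients, so at least one cytopenia may be common. The largest figure, 24.7%, belongs to the most extreme split and lowest prevalence examined, and falls to 7.3% if Levene's test chooses the row. Which row counts is a detail that an SAP may settle. No variable with three or more unordered levels is defined, and the protocol does not say that outcome is compared between waves.

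All of this stands as a limit on the harm: the inflation and the coding example are conditional illustrations, not expected results. It does not rescue the sentence. The protocol makes a positive choice of method for categorical variables, and that choice is wrong. This is not a detail left to an SAP. If the t test was really meant for normally distributed continuous data, the protocol names no test for categorical variables, and the same correction is needed.

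**Conclusion.** The concern holds. One of only two named tests does not match its data type, and no test of proportions is named. It must be fixed because a stated method is wrong, not because the main comparison has been shown to be distorted.

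For common two-level variables the correction would hardly change a p-value. It would matter for a rare category in unequal groups if the unequal-variance row is read, and for any categorical variable with three or more unordered levels. Unequal groups are plausible, since one wave is set against two combined, but the sizes of these effects depend on the assumed splits and prevalences. The error in the method does not depend on any of them.

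**What to change.** Replace the sentence on tests in the Statistical analysis section with:

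> Continuous variables will be compared by the Mann-Whitney U test; categorical variables by the chi-square test, or Fisher's exact test when any expected cell count is below 5.

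If an SAP exists, it should carry the same wording. The cost is one sentence: no new data and no change of software.
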